10.5. Appendix 5: Contraceptive and Barrier Guidance

Participants must follow contraceptive measures as outlined in Section 5.1, Inclusion Criteria. Pregnancy information will be collected and reported as noted in Section 8.2.5, Pregnancy Testing, Section 8.3.5, Pregnancy and Appendix 7: Adverse Events, Serious Adverse Events, Product Quality Complaints, and Other Safety Reporting: Definitions and Procedures for Recording, Evaluating, Follow-up, and Reporting.

Definitions

Woman of Childbearing Potential

A woman is considered fertile following menarche and until becoming postmenopausal unless permanently sterile (see below).

Woman Not of Childbearing Potential

• premenarchal

A premenarchal state is one in which menarche has not yet occurred.

postmenopausal

A postmenopausal state is defined as no menses for 12 months without an alternative medical cause.

If there is a question about menopausal status in women on HRT, the woman will be required to use one of the non-estrogen-containing hormonal highly effective contraceptive methods if she wishes to continue HRT during the study.

• permanently sterile (for the purpose of this study)

- Permanent sterilization methods include hysterectomy, or bilateral salpingectomy, or bilateral oophorectomy.
- Has congenital abnormalities resulting in sterility.

Note: If the childbearing potential changes after start of the study (eg, a premenarchal woman experiences menarche) or the risk of pregnancy changes (eg, a woman who is not heterosexually active becomes active), a woman must begin a highly effective method of contraception, as described throughout the inclusion criteria.

If reproductive status is questionable, additional evaluation should be considered.

Contraceptive (birth control) use by men or women must be consistent with local regulations regarding the acceptable methods of contraception for those participating in clinical studies.

Typical use failure rates may differ from those when used consistently and correctly. Use must be consistent with local regulations regarding the use of contraceptive methods for participants in clinical studies.

Examples of Contraceptives

EXAMPLES OF CONTRACEPTIVES^a ALLOWED DURING THE STUDY INCLUDE:

USER INDEPENDENT

Highly Effective Methods That Are User Independent *Failure rate of* <1% *per year when used consistently and correctly.*

- Intrauterine device (IUD)
- Tubal closure (eg, bilateral tubal occlusion, bilateral tubal ligation)
- Azoospermic partner (vasectomized or due to medical cause)
 (Vasectomized partner is a highly effective contraceptive method provided that the partner is the sole sexual partner of the woman of childbearing potential and the absence of sperm has been confirmed. If not, additional highly effective method of contraception must be used.

Spermatogenesis cycle is approximately 74 days.)

USER DEPENDENT

Highly Effective Methods That Are User Dependent *Failure rate of* <1% *per year when used consistently and correctly.*

Sexual abstinence

(Sexual abstinence is considered a highly effective method only if defined as refraining from heterosexual intercourse during the entire period of risk associated with the study intervention. The reliability of sexual abstinence needs to be evaluated in relation to the duration of the study and the preferred and usual lifestyle of the participant.)

NOT ALLOWED AS SOLE METHOD OF CONTRACEPTION DURING THE STUDY (not considered to be highly effective - failure rate of ≥1% per year)

- Any hormonal (estrogen and/or progestogen) contraceptives (oral, injectables, implants, patches, intrauterine hormone-releasing system (IUS), etc.)^b
- Male or female condom with or without spermicide^c
- Cap, diaphragm, or sponge with spermicide
- A combination of male condom with either cap, diaphragm, or sponge with spermicide (double barrier methods)^c
- Periodic abstinence (calendar, symptothermal, post-ovulation methods)
- Withdrawal (coitus-interruptus)
- Spermicides alone
- Lactational amenorrhea method (LAM)
- a) Typical use failure rates may differ from those when used consistently and correctly. Use must be consistent with local regulations regarding the use of contraceptive methods for participants in clinical studies.
- b) The interaction between JNJ-64281802 and hormone-based contraceptives has not been assessed. The efficacy of hormone-based contraceptives may be decreased when coadministered with JNJ-64281802 and therefore should not be considered a highly effective contraceptive method during dosing with JNJ-64281802. A woman using any type of hormonal contraception must use an additional barrier-based contraceptive method.
- c) Male condom and female condom must not be used together (due to risk of failure with friction).

CONFIDENTIAL – FOIA Exemptions Apply in U.S.

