For a participant >18 years old: between 90 and 140 mmHg systolic, extremes included, and ≤90 mmHg diastolic at screening.

Two repeat measurements are allowed in the absence of any other concerning health screening issues. If the results of blood pressure are outside these ranges, the participant may be included only if the investigator judges the deviations from normal blood pressure to be not clinically significant or to be appropriate and reasonable for the population under study.

Weight

- 4. Criterion modified per Amendment 1.
 - 4.1 Must have a body mass index (BMI, weight in kg divided by the square of height in meters) between 18.0 and 35.0 kg/m² inclusive, and a body weight of \geq 40.0 kg at screening.

Sex and Contraceptive/Barrier Requirements

- 5. Man or woman.
- 6. A woman must have a negative highly sensitive urine pregnancy test at screening.
- 7. Criterion modified per Amendment 3
 - 7.1 A woman must be (as defined in Appendix 5: Contraceptive and Barrier Guidance)

CONFIDENTIAL – FOIA Exemptions Apply in U.S.

- a. Not of childbearing potential.
- b. Of childbearing potential and practicing a highly effective, preferably user-independent method of contraception (failure rate of <1% per year when used consistently and correctly) and agrees to remain on a highly effective method while receiving study intervention and until ≥90 days after the last dose,

the end of relevant systemic exposure. The investigator should evaluate the potential for contraceptive method failure (eg, noncompliance, recently initiated) in relationship to the first dose of study intervention.

Examples of highly effective methods of contraception are provided in Appendix 5: Contraceptive and Barrier Guidance.

A woman using hormonal contraception must use an additional barrier-based contraceptive method.

Note: The interaction between JNJ-64281802 and hormone-based contraceptives has not been assessed. The efficacy of hormone-based contraceptives may be decreased when coadministered with JNJ-64281802 and therefore they should not be considered as a highly effective contraceptive method during dosing with JNJ-64281802.

- 8. A woman must agree not to donate eggs (ova, oocytes) or freeze for future use for the purposes of assisted reproduction during the study and for a period of 6 months after the last dose of study intervention.

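### Read in its ordinary sense, the HRT sentence in Protocol Appendix 5 asks for a hormonal method that counts as highly effective, a class the same appendix leaves empty; at best the sentence is ambiguous

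*Protocol*

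**What the plan says.** Four pieces of current protocol text bear on this.

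- **Appendix 5, definition of postmenopausal.** If menopausal status is in question in a woman on HRT, she will be "required to use one of the non-estrogen-containing hormonal highly effective contraceptive methods" as the condition for continuing HRT.
- **Appendix 5, table of examples.** Under the heading "NOT ALLOWED AS SOLE METHOD OF CONTRACEPTION DURING THE STUDY", which also describes these methods as not highly effective (failure rate of at least 1% per year), the first entry is "Any hormonal (estrogen and/or progestogen) contraceptives (oral, injectables, implants, patches, intrauterine hormone-releasing system (IUS), etc". Footnote b gives the reason: the interaction with the study drug has not been assessed, and hormone-based methods "should not be considered a highly effective contraceptive method during dosing with JNJ-64281802". It adds: "A woman using any type of hormonal contraception must use an additional barrier-based contraceptive method".
- **Section 5.1, criterion 7.1.** A woman must be either not of childbearing potential or "Of childbearing potential and practicing a highly effective, preferably user-independent method of contraception", and must stay on such a method until at least 90 days after the last dose. The criterion's note says hormone-based contraceptives may work less well with the study drug and "therefore they should not be considered as a highly effective contraceptive method during dosing with JNJ-64281802".
- **Section 6.8.** Stable HRT is allowed in postmenopausal women.

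Appendix 5 opens by deferring to the eligibility criteria: "Participants must follow contraceptive measures as outlined in Section 5.1, Inclusion Criteria". Criterion 7.1 in turn refers to Appendix 5 for its definitions.

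**The concern.** The HRT sentence is a participant-protection rule for women who might still be fertile. Taken literally, it sends them to progestogen-type contraception and calls it highly effective. Everywhere else the protocol withholds that description from hormonal methods. Section 2.3.1 states that the drug's effect on hormonal contraceptive efficacy is unknown, and footnote b says efficacy may be reduced. A site following the sentence word for word would choose from the one class the protocol distrusts. A site following the table would find no hormonal method that qualifies. At stake is clear contraceptive guidance for this group, not the trial's inference.

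**Working it through.** No arithmetic of the trial design is involved, and the plan states no figure to reproduce. The check sets the texts side by side.

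**1. What the sentence demands.** In ordinary English the method must have three properties: it is hormonal, it contains no estrogen, and it is highly effective.

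**2. What the appendix offers as highly effective.**

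| Method listed | Hormonal? |
|---|---|
| Intrauterine device | No; the hormone-releasing system is listed separately, among the methods not acceptable alone |
| Tubal closure | No |
| Azoospermic partner | No |
| Sexual abstinence | No |

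Hormonal methods among those listed: 0 of 4. The table gives examples and is not exhaustive, so an unlisted method has to be considered. The opposing list closes that route, because it covers any estrogen and/or progestogen contraceptive and ends its examples with an open-ended etc.

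**3. Over what period.** The opposing list applies during the study. Footnote b and the criterion 7.1 note apply during dosing. The duty in 7.1b lasts longest: with a last dose on Day 28, 28 + 90 = Day 118 at the earliest, which is 118 − 90 = 28 days after the Day 90 visit. The HRT sentence gives no contraceptive period of its own beyond a reference to continuing HRT during the study.

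**4. Does the added barrier repair it?** It reduces risk but does not change the classification. Condoms, caps, diaphragms and sponges are on the same not-highly-effective list, and the protocol nowhere says that a hormonal method plus a barrier becomes highly effective.

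**5. Is there a reading that fits?** Yes. If the adjectives are grouped differently, the sentence could mean highly effective methods other than estrogen-containing hormonal ones. All 4 listed methods would then qualify. This is the less natural parse, and it leaves the word hormonal doing odd work, but it agrees with the table and with 7.1b.

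**6. Where the sentence sits.** It appears under the definition of women not of childbearing potential, although it concerns a woman whose membership of that group is in doubt. The appendix's own rule is that a woman counts as fertile until she is postmenopausal, unless permanently sterile, which would put her under 7.1b.

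**The case against.** The strongest reply has three parts.

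First, the alternative parse removes the contradiction and may be what the sponsor meant. This stands in part. It rules out saying flatly that no method can meet the requirement, a conclusion a reader might draw from the 0 of 4 count. It does not rescue the wording, because a site should not need the less natural reading to comply.

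Second, Section 5.1 governs. Appendix 5 does defer to it, but 7.1 relies on Appendix 5 for its definitions, and the position of the HRT sentence invites a site to treat this woman as not of childbearing potential and so outside 7.1b. The deferral helps without fully curing the problem.

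Third, the safeguards are real. Hormonal methods are barred only as a sole method, so a woman who took a progestogen because of this sentence would have to add a barrier. Further evaluation is advised when reproductive status is questionable, questions about the criteria go to the sponsor before enrolment (Section 5), and all women are pregnancy-tested at screening, on Days 28 and 50, and at any withdrawal visit (Section 8.2.5). All of this stands. A reader might infer that the sentence leaves these women relying on a hormonal method alone; the documents do not support that.

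**Conclusion.** This is an internal inconsistency in current protocol text, and a minor one. On the ordinary reading the HRT sentence conflicts with the Appendix 5 list throughout the study, and with footnote b and the 7.1 note during dosing. On the strained reading it is merely unclear. It needs rewording either way.

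The size is small. Only women on HRT with doubtful menopausal status are reached; their number is not given, and Section 6.8 allows HRT only in postmenopausal women. Each woman who completes the study has 3 scheduled pregnancy tests. It would be wrong to infer any effect on the efficacy or safety results: no endpoint, estimand, analysis or sample-size assumption depends on the sentence. SAP Section 1 records that the study ended on 02 October 2024, so the correction mainly serves any reuse of this text.

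The conclusion rests on taking the sentence in its ordinary grammatical sense and on the protocol not treating hormonal plus barrier as highly effective, which it nowhere does.

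**What to change.** Replace the sentence in Appendix 5 with: *If there is a question about menopausal status in a woman on HRT, she must follow criterion 7.1b and use one of the non-hormonal highly effective methods listed in this appendix (IUD, tubal closure, azoospermic partner, or sexual abstinence) during dosing and for at least 90 days after her last dose, if she wishes to continue HRT.*

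Add a cross-reference to this sentence from the HRT allowance in Section 6.8, which now speaks only of postmenopausal women and so does not clearly cover a woman whose status is in doubt.

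The cost is one sentence and one cross-reference, with no effect on sample size, endpoints or analysis. The disadvantage is that the rule is slightly stricter than progestogen plus barrier for this small group, if the sponsor regards that combination as acceptable under 7.1. In that case the change alters practice and belongs in an amendment; the clarification communication described in Section 10.6.1 is reserved for wording that leaves study conduct unchanged.

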10.6. Appendix 6: Regulatory, Ethical, and Study Oversight Considerations

10.6.1. Regulatory and Ethical Considerations

Investigator Responsibilities

The investigator is responsible for ensuring that the study is performed in accordance with the protocol, current International Council for Harmonisation of Technical Requirements for Pharmaceuticals for Human Use (ICH) guidelines on GCP, and applicable regulatory and country-specific requirements.

Good Clinical Practice is an international ethical and scientific quality standard for designing, conducting, recording, and reporting studies that involve the participation of human participants. Compliance with this standard provides public assurance that the rights, safety, and well-being of study participants are protected, consistent with the principles that originated in the Declaration of Helsinki, and that the study data are credible.

Protocol Clarification Communications

If text within a final approved protocol requires clarification (eg, current wording is unclear or ambiguous) that does not change any aspect of the current study conduct, a protocol clarification communication (PCC) may be prepared. The PCC Document will be communicated to the Investigational Site, Site Monitors, Local Trial Managers, Clinical Trial Managers, and/or Contract Research Organizations who will ensure that the PCC explanations are followed by the investigators.

The PCC Document may be shared by the sites with IECs/IRBs per local regulations.

The PCC Documents must NOT be used in place of protocol amendments, but the content of the PCC Document must be included in any future protocol amendments.

Protocol Amendments

Neither the investigator nor the sponsor will modify this protocol without a formal amendment by the sponsor. All protocol amendments must be issued by the sponsor, and signed and dated by the investigator. Protocol amendments must not be implemented without prior IEC/IRB approval, or when the relevant competent authority has raised any grounds for non-acceptance, except when necessary to eliminate immediate hazards to the participants, in which case the amendment must be promptly submitted to the IEC/IRB and relevant competent authority. Documentation of amendment approval by the investigator and IEC/IRB must be provided to the sponsor. When the change(s) involve only logistic or administrative aspects of the study, the IEC/IRB (where required) only needs to be notified.

In situations where a departure from the protocol is unavoidable during the study, the investigator or other physician in attendance will contact the appropriate sponsor representative listed in the Contact Information page(s), which will be provided as a separate document. Except in emergency situations, this contact should be made before implementing any departure from the protocol. In

all cases, contact with the sponsor must be made as soon as possible to discuss the situation and agree on an appropriate course of action. The data recorded in the CRF and source documents will reflect any departure from the protocol, and the source documents will describe this departure and the circumstances requiring it.

Regulatory Approval/Notification

This protocol and any amendment(s) must be submitted to the appropriate regulatory authorities in each respective country, if applicable. A study may not be initiated until all local regulatory requirements are met.

Required Prestudy Documentation

The following documents must be provided to the sponsor before shipment of study intervention to the study site:

- Protocol and amendment(s), if any, signed and dated by the principal investigator.
- A copy of the dated and signed (or sealed, where appropriate per local regulations), written IEC/IRB approval of the protocol, amendments, ICF, any recruiting materials, and if applicable, participant compensation programs. This approval must clearly identify the specific protocol by title and number and must be signed (or sealed, where appropriate per local regulations) by the chairman or authorized designee.
- Name and address of the IEC/IRB, including a current list of the IEC/IRB members and their function, with a statement that it is organized and operates according to GCP and the applicable laws and regulations. If accompanied by a letter of explanation, or equivalent, from the IEC/IRB, a general statement may be substituted for this list. If an investigator or a member of the study site personnel is a member of the IEC/IRB, documentation must be obtained to state that this person did not participate in the deliberations or in the vote/opinion of the study.
- Regulatory authority approval or notification, if applicable.
- Signed and dated statement of investigator (eg, Form FDA 1572), if applicable.
- Documentation of investigator qualifications (eg, curriculum vitae).
- Completed investigator financial disclosure form from the principal investigator, where required.
- Signed and dated Clinical Trial Agreement, which includes the financial agreement.
- Any other documentation required by local regulations.

The following documents must be provided to the sponsor before enrollment of the first participant:

- Completed investigator financial disclosure forms from all subinvestigators.
- Documentation of subinvestigator qualifications (eg., curriculum vitae).
- Name and address of any local laboratory conducting tests for the study, and a dated copy of current laboratory normal ranges for these tests, if applicable.

• Local laboratory documentation demonstrating competence and test reliability (eg, accreditation/license), if applicable.

Independent Ethics Committee or Institutional Review Board

Before the start of the study, the investigator (or sponsor where required) will provide the IEC/IRB with current and complete copies of the following documents (as required by local regulations):

- Final protocol and, if applicable, amendments.
- Sponsor-approved ICF (and any other written materials to be provided to the participants).
- IB (or equivalent information) and amendments/addenda.
- Sponsor-approved participant recruiting materials.
- Information on compensation for study-related injuries or payment to participants for participation in the study, if applicable.
- Investigator's curriculum vitae or equivalent information (unless not required, as documented by the IEC/IRB).
- Information regarding funding, name of the sponsor, institutional affiliations, other potential conflicts of interest, and incentives for participants.
- Any other documents that the IEC/IRB requests to fulfill its obligation.

This study will be undertaken only after the IEC/IRB has given full approval of the final protocol, amendments (if any, excluding the ones that are purely administrative, with no consequences for participants, data or study conduct, unless required locally), the ICF, applicable recruiting materials, and participant compensation programs, and the sponsor has received a copy of this approval. This approval letter must be dated and must clearly identify the IEC/IRB and the documents being approved.

Approval for the collection of optional samples for research and for the corresponding ICF must be obtained from the IEC/IRB. Approval for the protocol can be obtained independent of this optional research component.

During the study the investigator (or sponsor where required) will send the following documents and updates to the IEC/IRB for their review and approval, where appropriate:

- Protocol amendments (excluding the ones that are purely administrative, with no consequences for participants, data or study conduct).
- Revision(s) to ICF and any other written materials to be provided to participants.
- If applicable, new or revised participant recruiting materials approved by the sponsor.
- Revisions to compensation for study-related injuries or payment to participants for participation in the study, if applicable.
- New edition(s) of the IB and amendments/addenda.

- Summaries of the status of the study at intervals stipulated in guidelines of the IEC/IRB (at least annually).
- Reports of AEs that are serious, unlisted/unexpected, and associated with the study intervention.
- New information that may adversely affect the safety of the participants or the conduct of the study.
- Deviations from or changes to the protocol to eliminate immediate hazards to the participants.
- Report of deaths of participants under the investigator's care.
- Notification if a new investigator is responsible for the study at the site.
- Development Safety Update Report and Line Listings, where applicable.
- Any other requirements of the IEC/IRB.

For all protocol amendments (excluding the ones that are purely administrative, with no consequences for participants, data or study conduct), the amendment and applicable ICF revisions must be submitted promptly to the IEC/IRB for review and approval before implementation of the change(s).

At least once a year, the IEC/IRB will be asked to review and reapprove this study, where required.

At the end of the study, the investigator (or sponsor where required) will notify the IEC/IRB about the study completion.

Country Selection

This study will only be conducted in those countries where the intent is to launch or otherwise help ensure access to the developed product if the need for the product persists, unless explicitly addressed as a specific ethical consideration in Section 4.2.1, Study-specific Ethical Design Considerations.

Other Ethical Considerations

For study-specific ethical design considerations, refer to Section 4.2.1, Study-specific Ethical Design Considerations.

